
Immunogenicity
 
Immunogenicity of SP0202 formulations and Prevnar 13 will be assessed through the measurement of serotype specific type G immunoglobulin (IgG) and opsonophagocytic activity (OPA) of pneumococcal serotypes. IgG concentrations for all pneumococcal serotypes included in each of the SP0202 formulations and Prevnar 13 will be measured in all subjects. OPA will be measured in all toddlers enrolled in Stage I and in a random subset of 125 infants per group (depending on the available serum volume) enrolled in Stage II in samples collected 1 month after Dose 3, and pre- and post-dose (PD) 4.
 
For toddlers, the immunogenicity of Pentacel will be assessed 1 month after injection. For infants, the immunogenicity of concomitant vaccines will be assessed 1 month after the last injection in the study, ie, 1-month PD3 for Pentacel, ENGERIX-B*, and RotaTeq; 1-month PD4 for M-M-R_{II} and VARIVAX.
 
* Immunogenicity to ENGERIX-B will be presented according to the number of doses received
 
Safety
 
Reactogenicity data will be collected in all subjects after each injection. Injection site reactions will be collected for both study and concomitant pediatric vaccines.
 
All subjects will be observed for 30 minutes after vaccination, and clinical site personnel will record any unsolicited systemic adverse events (AEs) occurring during that time as immediate unsolicited systemic AEs in the case report book (CRB).
 
Subjects' parents / guardians will record in the diary card (DC) / electronic DC (eDC) information about AEs (solicited and unsolicited), concomitant medications, and any medical visits or hospitalizations.
 
Solicited injection site and systemic reactions will be collected from D0 to D7 following injection. Unsolicited events will be collected from D0 to D30 following injection. Serious adverse events (SAEs) and adverse events of special interest (AESIs) will be collected throughout the study (from D0 until the 6-month follow-up safety phone contact).
 
At Visit 2 (V02) for toddlers and Visit 5 (V05) for infants, all parents / guardians will be given a memory aid (MA) in which to record safety information. At approximately 6 months after injection, the clinical site personnel will contact each subject's parents / guardians by phone to obtain information about SAEs and AESIs
	
The safety of investigational products will be continuously monitored by the Sponsor. An ESDR will be performed, the goal of which is to allow for a cautious, stepwise approach to vaccine administration.
 
The safety data collected will be entered into the CRB and summarized by the Sponsor. A blinded review will be performed by the Sponsor during the Safety Management Team (SMT) meetings. An unblinded review by the independent DMC will also be conducted. It is understood that this review is based on

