5.2.10 Conditions for Withdrawal

Parents / Guardians will be informed that they have the right to withdraw their child from the study at any time. A subject may be withdrawn from the study:

- At the discretion of the Investigator or Sponsor due to safety concerns or significant non-compliance with the protocol (based on the Investigator's judgment), without the subject's permission (withdrawal)
- At the request of the parent / guardian (dropout)

The reason for a withdrawal or dropout should be clearly documented in the source documents and in the CRB.

The Investigator must determine whether voluntary withdrawal is due to safety concerns (in which case, the reason for discontinuation will be noted as "Adverse Event") or for another reason.

Withdrawn subjects will not be replaced.

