6.5 Randomization and Allocation Procedures

On the day of enrollment, subjects who meet the inclusion/exclusion criteria and sign the ICF will be randomly assigned to Groups 1 through 4 in a 1:1:1:1 ratio to have approximatively 140 subjects (35 subjects in each treatment group) for toddlers subjects (Stage I) or to Group 5 through 8 in a 1:1:1:1 ratio to have approximatively 700 subjects (175 subjects in each treatment group) for infants subjects (Stage II). Stage II randomization will be at least stratified by country.

Following DMC assessment, in case one or more of the SP0202 formulations may not be included in the stage II, the randomization list will match with the selected groups for stage II; the sample size of each group will remain unchanged (175 subjects by group) and the ratio between groups will be balanced.

Site staff will connect to the IRT, enter the identification and security information, and confirm a minimal amount of data in response to IRT prompts. The IRT will randomize the subjects and then provide the vaccine assignment and have the site staff confirm it. The full detailed procedures for group allocation are described in the Operating Guidelines. If the subject is not eligible to participate in the study, then the information will only be recorded on the subject recruitment log.

IRT will also be used to randomly allocate subject to the OPA subset in Stage II (around 125 infants by group). This allocation has no impact on the study conduct on site; the list of selected subjects will be communicated to the laboratory personnel.

Subject numbers that are assigned by the IRT will consist of a 12-digit string (a 3-digit country identifier, a 4-digit study center identifier, and a 5-digit subject identifier). The first digit of the subject identifier will be '1' for toddlers subjects randomized into Stage 1 and '2' for infants subjects randomized into Stage 2. For example, Subject 840000110005 is the fifth toddler subject enrolled in Center Number 1 in the US in stage I (840 being the US country code), and Subject 840000120005 is the fifth infant subject enrolled in Center Number 1 in the US (840 being the US country code).

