12.2 Analysis Sets

12.2.1 Full Analysis Set

Three FAS will be defined: one for Toddlers (FAS1), one for Infants at Primary series (ie, after 3 doses) (FAS2) and one for Infants at Booster (FAS3):

- The full analysis set (FAS)1 – Toddlers: is defined as the subset of randomized subjects to Groups 1 to 4 who received at least 1 dose of the study vaccine and had a valid post-vaccination blood sample result (serotype specific IgG concentration or serotype specific OPA titer for at least 1 serotype, or titer/concentration for at least one antigen on the concomitant vaccines)
- The FAS2 – Infants: is defined as the subset of randomized subjects to Groups 5 to 8 who received at least 1 dose of the study vaccine in the primary series and had a valid post-primary series vaccination blood sample result (serotype specific IgG concentration or serotype specific OPA titer for at least 1 serotype, or titer/concentration for at least one antigen on the concomitant vaccines)
- The FAS3 – Infants: is defined as the subset of randomized subjects to Groups 5 to 8 who received at least 1 dose of the study vaccine at the time of booster and had a valid post-booster vaccination blood sample result (serotype specific IgG concentration or serotype specific OPA titer for at least 1 serotype, or titer/concentration for at least one antigen on the concomitant vaccines)

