12.5 Determination of Sample Size and Power Calculation

The number of subjects is designed to provide immunogenicity and safety data on the 3 SP0202 formulations and on Prevnar 13 after each and any injection, as applicable in toddlers, and infants.

The sample size was set at 35 subjects per group (140 toddlers) in Stage I and 175 subjects per group (700 infants) in Stage II. Assuming a drop-out rate of approximatively 10% in the toddlers, 20% (PD3) and 30% (PD4) in infants, a total of 31, 140, and 122 evaluable subjects per group is anticipated for toddlers, infants at PD3, and infants at PD4, respectively.

13 Ethical and Legal Issues and Investigator / Sponsor Responsibilities

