Following DMC recommendations after Stage I early safety data review (ESDR), any SP0202 formulation may be excluded from entering Stage II of the study if considered not adequate for further evaluation in infants. In such a case, the number of groups to entered Stage II will be adjusted accordingly and the planned sample size in each selected group will be kept.

An Interactive Response Technology (IRT) will be used to assign participant numbers and study group at each clinical site.

Over the study period of Stage I (Group 1 to 4), toddlers will attend 2 planned visits at D0 and D30. Two blood samples (BL) of 6 mL each will be collected for the assessment of the immunogenicity of the 3 SP0202 formulations, Prevnar 13 and Pentacel: before injection of PCV (BL0001) at D0 (Visit 1 [V01]) and 1 month after PCV injection (BL0002) at D30 (V02).

Over the study period of Stage II (Group 5 to 8), infants will attend 6 planned visits at D0, D60, D120, D150, D300-390, and D330-420. Overall, 3 or 4 BL will be collected for the assessment of the immunogenicity of the 3 SP0202 formulations, Prevnar 13 and pediatric vaccines: before injection of PCV (BL0001; 3 mL) at D0 (V01)\*, 1 month after PCV Dose 3 (BL0002; 6 mL) at D150 (V04), before PCV Dose 4 (BL0003; 6 mL) at D300 (V05), and 1 month after PCV Dose 4 (BL0004; 6 mL) at D330 (V06).

The study vaccine-related immunogenicity assessments will involve both the measurement of serotype specific IgG concentrations and of OPA titers. IgG concentrations for all pneumococcal serotypes included in each of the SP0202 formulations and Prevnar 13 will be measured in all participants. The evaluation of the IgG concentrations will be made using the international standard reference serum 007sp that includes assignment for all serotypes included in SP0202. OPA will be measured in all available samples from Stage 1 and on a subset of Stage 2 samples.

The immunogenicity of the pediatric vaccines administered concomitantly with the study vaccines will be assessed using standard assays for the respective antigens.

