## 5.2 Analysis Sets

Three analysis sets will be used: The Per-Protocol Analysis Set, the Full Analysis Set, and the Safety Analysis Set.

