## 5.5 Determination of Sample Size and Power Calculation

The number of participants is designed to provide immunogenicity and safety data on the 3 SP0202 formulations and on Prevnar 13 after each and any injection, as applicable in toddlers, and infants.

The sample size was set at 35 participants per group (140 toddlers) in Stage I and 175 participants per group (700 infants) in Stage II. Assuming a drop-out rate of approximatively 10% in the toddlers, 20% (PD3) and 30% (PD4) in infants, a total of 31, 140, and 122 evaluable participants per group is anticipated for toddlers, infants at PD3, and infants at PD4, respectively.

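### Does the infant OPA subset of about 125 per group fall short because the plan does not say when it is drawn?

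*Protocol*

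**What the plan says.** Protocol 6.5 describes the subset in one sentence, "IRT will also be used to randomly allocate subject to the OPA subset in Stage II (around 125 infants by group"), and adds that sites are unaffected and that the laboratory receives the list. It gives no visit or trigger for the draw. The reference to the day of enrollment in that section concerns assignment to vaccine group, and the infant procedure tables show IRT contacts at V01, V02, V03 and V05.

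The synopsis sets the infant OPA time points at PD3, pre-Dose 4 and PD4 and describes the measurement as made "in a random subset of 125 infants per group (depending on the available serum volume) enrolled in Stage II in samples collected 1 month" (the sentence goes on to list those time points).

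On attrition, Protocol 12.5 reads "Assuming a drop-out rate of approximatively 10% in the toddlers, 20% (PD3) and 30% (PD4) in infants". SAP 5.5 repeats these rates and concludes that "a total of 31, 140, and 122 evaluable participants per group is anticipated" (toddlers, infants at PD3, infants at PD4). Both statements concern the full groups. Protocol 5.2.10 says "Withdrawn subjects will not be replaced".

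The SAP gives the subset no size. Section 3.1 says "OPA will be measured in all available samples from Stage 1 and on a subset of Stage 2 samples", and section 5.2 says "Three analysis sets will be used: The Per-Protocol Analysis Set, the Full Analysis Set, and the Safety Analysis Set", with no separate OPA set. SAP 5.1.2.2.2 and Table 5.3 do, however, restrict each infant OPA analysis to the OPA subset.

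**The concern.** The number 125 appears beside allocation in Protocol 6.5 and beside measurement in the synopsis. The two agree only if nobody drops out, and the plan assumes that many will. Because the sentence stands in the randomization section, a reader may infer a draw at enrollment. On that reading the subset shrinks to about 100 at PD3 and 87 at PD4. If 125 is instead read as the number with results, it cannot be met at PD4, where only 122 infants per group are expected in all.

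Two of the three OPA secondary objectives, the infant PD3 and PD4 responses, rest on this subset. They cover 21 serotypes and include GMT ratios between groups. What is at stake is how precise those results will be and whether a reader can tell in advance.

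**Working it through.** **Inputs.** 175 infants per group and drop-out of 20% at PD3 and 30% at PD4 (Protocol 12.5, SAP 5.5); 10% drop-out from 35 toddlers per group (same sections); about 125 per group in the OPA subset (Protocol 6.5). Response rates and log10 standard deviations are not in the documents, so ranges are assumed below.

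**The plan's own figures.** Evaluable n = enrolled n × (1 − drop-out):
- toddlers: 35 × 0.90 = 31.5 (stated 31)
- infants at PD3: 175 × 0.80 = 140 (stated 140)
- infants at PD4: 175 × 0.70 = 122.5 (stated 122)

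All three reproduce, with halves rounded down.

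**Draw at enrollment, with the same drop-out in the subset.**
- PD3: 125 × 0.80 = 100
- PD4: 125 × 0.70 = 87.5

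**Draw from the roughly 140 infants reaching PD3.**
- PD3: 125
- PD4: 125 × 122.5/140 = 109.4 if drop-out is cumulative; 125 × 0.70 = 87.5 if missing V04 says nothing about attending for PD4

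**125 read as the number with results.** At PD3, 140 are available, so it can be met. At PD4, 122 are available, a shortfall of 3 in 125, or 2.4%, against a figure that Protocol 6.5 itself gives as approximate.

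**Precision.** Half-widths of the Clopper-Pearson 95% interval for the percentage at or above LLOQ, in points, for assumed rates of 50%, 80% and 90%. The last two columns give the factor by which the 95% limits of a two-group GMT ratio lie above and below the estimate, 10^(1.96 × SD × √(2/n)), for an assumed log10 SD of 0.4 or 0.8.

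| n per group | 50% | 80% | 90% | SD 0.4 | SD 0.8 |
|---|---|---|---|---|---|
| 125 | 9.1 | 7.4 | 5.7 | 1.26 | 1.58 |
| 109 | 9.7 | 7.9 | 6.1 | 1.28 | 1.63 |
| 100 | 10.2 | 8.3 | 6.4 | 1.29 | 1.67 |
| 87 | 10.9 | 8.8 | 6.9 | 1.31 | 1.73 |

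Relative to 125, the log-scale interval for a GMT widens by √(125/100) = 1.118 with 100 results and by √(125/87) = 1.199 with 87.

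**What a later draw could gain.** The width ratio is √(100/125) = √(87.5/109.4) = 0.894, so intervals would be about 11% narrower at best. In full Clopper-Pearson width:
- at 90%: 12.7 against 11.5 points at PD3, and 13.9 against 12.2 at PD4
- at 50%: 20.3 against 18.1 points at PD3, and 21.8 against 19.5 at PD4

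The best case is therefore 1.2 to 2.3 points.

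**What it would cost.** Extra sera over four groups: PD3 4 × 25 = 100; PD4 4 × 21.9 = 87.5; pre-Dose 4 between 87.5 and 100. The total is 275 to 287.5.

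**The case for a change.** The strongest argument for a change is that the trial is meant to help choose a formulation for Phase III (Protocol 1.4), that OPA contributes to that picture, and that a reader should know whether about 87, 109 or 122 infants per group stand behind the PD4 results. Read as a count of measurements at each time point, the synopsis figure conflicts with the plan's own drop-out at PD4. A sentence in each document would settle the matter.

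Part of this stands. Neither document, as supplied, gives the time of the draw or an expected OPA number, and 100 and 87.5 are right if the draw is made at enrollment.

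The rest does not make an error:
- Protocol 6.5 attaches 125 to allocation, and the synopsis qualifies it by serum volume. Both fit one nominal subset size that will yield somewhat fewer results. Nothing calls it evaluable.
- The non-replacement rule in Protocol 5.2.10 is about withdrawal from the trial. It does not say whether the laboratory list may be topped up.
- Analysts need no further set: SAP 5.2.5 names the PPAS and then the FAS, and Table 5.3 limits the infant OPA rows to the subset, so the analysis is the subset within each.
- Protocol 6.5 refers group allocation to the Operating Guidelines, which are not available here, and parts of the assay and interim-analysis sections are not shown. The timing may be given there.

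Drawing after V04 is also not plainly better. It would lose no PD3 result, because FAS2 already requires that an infant "had a valid post-primary series vaccination blood sample result". FAS3 has no such requirement, however, and Protocol 5.1.4 lets infants without a V04 sample continue, so some FAS3 infants could never have a PD4 OPA result. The 11% is an upper bound for a further reason: PPAS2 excludes some infants who have a V04 sample, such as those sampled or vaccinated out of window, so 125 sample-holders may give fewer than 125 per-protocol results.

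**Conclusion.** No change is needed. The documents leave out when the subset is drawn, but no stated figure is wrong. The evaluable counts for the full groups reproduce, no OPA-evaluable count or precision target is given that could be missed, and no hypothesis is tested.

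An allocation of about 125 made at random gives valid descriptive estimates and intervals at whichever visit it is made, subject to the same kind of attrition as the IgG results. SAP Table 5.1 requires numbers as well as percentages of participants for the threshold endpoints, so readers will be able to see how many infants contribute.

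The effect is on width alone. At PD3 between 100 and 125 infants per group can be expected, and at PD4 between about 87 and 109, depending on the draw. This assumes that drop-out in the subset matches the plan's rates and that serum volume removes no more. The most that a later draw could recover is about 11% of interval width, and that only if the draw is now at enrollment, which is an inference. Set against about 275 to 290 further sera and the loss of some PD4 results, it is a choice for the sponsor and not a correction.

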6.6 Treatment Compliance

The following measures will ensure that the vaccine doses administered comply with those planned, and that any non-compliance is documented so that it can be accounted for in the data analyses:

- All vaccinations will be administered by qualified study personnel
- The person in charge of product management at the site will maintain accountability records of product delivery to the study site, product inventory at the site, dose(s) given to each subject, and the disposal of unused or wasted doses

6.7 Concomitant Medications and Other Therapies

At the time of enrollment, ongoing medications and other therapies (eg, blood products) should be recorded in the source document as well as new medications prescribed for new medical conditions / AEs during study participation.

Documentation in the CRB of ongoing concomitant medication(s) will be limited to specific categories of medication(s) of interest beginning on the day of first vaccination. This may include medications of interest that were started prior to the day of vaccination.

Reportable medications will be collected in the CRB from the day of each vaccination to the end of the solicited and unsolicited follow-up period.

Reportable medications include medications that impact or may impact the consistency of the safety information collected after any vaccination and/or the immune response to vaccination. Three standard categories of reportable medications are defined:

- Category 1: medications impacting or that may have an impact on the evaluation of the safety (eg, antipyretics, analgesics, and non-steroidal anti-inflammatory drugs [NSAIDs], steroids/corticosteroids [therapy duration for less than 2 consecutive weeks])

Note: Topical steroids (Inhaled, otic, ophthalmic, nasal etc.) should not be captured or reported.

- Category 2: medications impacting or that may have an impact on the immune response (eg, other vaccines [including influenza vaccine in the 2 weeks [14 days] preceding or following any study vaccination], blood products, antibiotic classes taken within 3 days [72 hours] prior to blood draw that may interfere with bioassays used by the GCI department, immune-suppressors, immune-modulators with immunosuppressive properties, anti-proliferative drugs such as DNA synthesis inhibitors, immune globulins preceding in the 3 months preceding any vaccination for infants)

Note: Topical antibiotics (Inhaled, otic, ophthalmic, nasal, etc.) should not be captured or reported.

- Category 3: medications impacting or that may have an impact on both the safety and the immune response (eg, long-term systemic corticosteroid therapy [prednisone or equivalent for more than 2 consecutive weeks])

Note: Topical steroids (Inhaled, otic, ophthalmic, nasal etc.) should not be captured or reported.

The information reported in the CRB for each reported medication will be limited to:

- Trade name for a medication composed of several molecules OR international nonproprietary name (INN) for a medication composed of one single molecule
- Origin of prescription: prophylaxis Yes/No. Medication(s) prescribed for AE prophylaxis will be recorded in the Action Taken of the AE collection tables.
- Medication category (1, 2, or 3)
- Start and stop dates

Dosage and administration route, homeopathic medication, topical and inhaled steroids, as well as topical, ophthalmic, and ear treatments will not be recorded. Topical analgesics should not be applied at the site of vaccination; however, if they are applied inadvertently to the vaccination site, they should be recorded as a Category 1 medication in this specific instance.

Medications given in response to an AE will be captured in the “Action Taken” section of the AE CRF only. No details will be recorded in the concomitant medication CRF unless the medication(s) received belongs to one of the prelisted categories. Medications will not be coded.

7 Management of Samples

Blood samples for the assessment of antibody responses will be collected at V01 and V02 for toddlers; at V01^a, V04, V05, and V06 for infants. See the Table of Study Procedures and [Section 5.1.3](#) for details of the sampling schedule.

